**Table 4: Analysis set**

Analysis set	Definition
Enrolled analysis set	All study participants who signed the informed consent form (including screening failures).
Evaluable for response set	Cohort A: All study participants with measurable baseline disease who received at least 1 dose of study intervention.  Cohort B: All study participants with measurable disease and/or unfavourable CTC count at baseline who received at least 1 dose of study intervention.
[a] Molecularly eligible centrally confirmed set	All molecularly eligible and centrally confirmed participants who received at least 1 dose of study intervention.

[a]Molecularly eligible centrally confirmed evaluable for response set
	
Cohort A: All molecularly eligible and centrally confirmed study participants with measurable baseline disease who received at least 1 dose of study intervention.
 
Cohort B: All molecularly eligible and centrally confirmed study participants with measurable disease and/or unfavourable CTC count at baseline who receive at least 1 dose of study intervention.

CCI [REDACTED]
	
CCI [REDACTED]

CCI [REDACTED]
	
CCI [REDACTED]

Safety set
	
All participants who received at least 1 dose of study intervention.

Interim analysis set
	
All participants in the molecular eligible centrally confirmed evaluable for response set with a chance to have at least two follow up RECIST assessments (i.e. all patients who received first dose of ceralasertib, at least 16 weeks prior to the data cut off date).

[a] Please refer to the latest CSP for more details regarding central confirmation. A separate specification document will be provided to support the programming of the ‘centrally confirmed’ flag.

Upon database release, protocol deviation and analysis set outputs will be produced and will be sent to AZ for review. Prior to database lock, analysis set classification meeting will be arranged to discuss the outputs and decide which participants and/or participant data will be excluded from certain analyses. Decisions made regarding the exclusion of participants and/or participant data from analyses will be made prior to database hard lock and will be documented and approved by AZ.

A summary on which analysis set will be used for each outcome variable is provided in [Table 5](#) (Cohort A) and [Table 6](#) (Cohort B).

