**Table 6: Summary of outcome variables and analysis sets for Cohort B**

Outcome Variable	Analysis Set
Study Population/Demography Data	
Disposition of participants	All Enrolled
Demography characteristics	Safety set
Baseline and disease characteristics	Safety set
Important protocol deviations	Safety set
Medical/surgical history	Safety set
Previous anti-cancer therapy	Safety set
Previous radio therapy	Safety set
Concomitant medications/procedures/radiotherapy	Safety set
Efficacy Data	
Composite response rate	Molecularly eligible centrally confirmed evaluable for response set Evaluable for response set Interim analysis set i
Duration of composite response	Molecularly eligible centrally confirmed evaluable for response set Evaluable for response set‡ Interim analysis set i
Percentage Change in tumour size	Molecularly eligible centrally confirmed evaluable for response set Evaluable for response set◇ Interim analysis set i
Radiological ORR/BoR	Molecularly eligible centrally confirmed evaluable for response set Evaluable for response set Interim analysis set i

Outcome Variable	Analysis Set
Duration of radiological response	Molecularly eligible centrally confirmed evaluable for response set Evaluable for response set‡ Interim analysis set I
rPFS	Molecularly eligible centrally confirmed set Safety set Interim analysis set I
PSA	Molecularly eligible centrally confirmed set Safety set* Interim analysis set I
CTC conversion	Molecularly eligible centrally confirmed evaluable for response set Evaluable for response set* Interim analysis set I
CCI	
CCI	CCI
Safety Data	
Exposure	Safety set
AEs	Safety set
Laboratory measurements	Safety set
Vital signs	Safety set
Physical examination	Safety set
Eastern Cooperative Oncology Group performance status (ECOG PS)	Safety set

\* CCI

‡ Only swimmer plot will be provided for this analysis set.

◊ Only spider plot will be provided for this analysis set.

IThis analysis set will be used only for interim analysis summary.

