**Target Lesions (TLs) – site investigator data**

Measurable disease is defined as having at least one measurable lesion, not previously irradiated, which is  $\geq 10$  mm in the longest diameter (LD) (except lymph nodes which must have short axis  $\geq 15$  mm) with computed tomography (CT) or magnetic resonance imaging (MRI) and which is suitable for accurate repeated measurements. A participant can have a maximum of 5 measurable lesions recorded at baseline with a maximum of 2 lesions per organ (representative of all lesions involved and suitable for accurate repeated measurement) and these are referred to as target lesions (TLs). If more than one baseline scan is recorded, then measurements from the one that is closest and prior to first dose/administration of study medication will be used to define the baseline sum of TLs. It may be the case that, on occasion, the largest lesion does not lend itself to reproducible measurement in which circumstance the next largest lesion, which can be measured reproducibly, should be selected.

All other lesions (or sites of disease) not recorded as TL should be identified as NTLs at baseline. Measurements are not required for these lesions, but their status should be followed at subsequent visits.

Note: For participants who do not have measurable disease at entry (i.e., no TLs) but have non-measurable disease, evaluation of overall visit responses will be based on the overall NTL assessment and the absence/presence of new lesions. If a participant does not have measurable disease at baseline, then the TL visit response will be not applicable (NA).

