***Evaluation of Bone progression status***

Bone lesions will be assessed by bone scan and will not be part of the RECIST v1.1 malignant soft tissue assessment. Bone lesions identified on a whole-body isotopic bone scan at baseline should be recorded and followed by the same method as per baseline assessment.

In this study isotopic bone scans will be used as a method of assessment to identify the presence of new bone lesions at post-baseline follow-up visits regardless of scheduled or unscheduled. New lesions will be recorded where a positive and unequivocal hot-spot that was not present on the baseline scan assessment is identified on a bone scan performed at any time during the study. The investigator should consider the positive hot-spot to be a significant new site of malignant disease and represent true disease progression in order to record the new lesion.

Baseline radiological tumour assessments are to be performed no more than 28 days before the first dose/administration of study medication and ideally as close as possible to the start of study treatment. Tumour assessments are then performed every 8 weeks ( $\pm 1$  week) following Cycle 1 Day 1 of the study treatment up to 1 year, then every 12 weeks ( $\pm 1$  week) until radiographic disease progression as defined by RECIST 1.1. (soft tissue; refer to [section 4.9.1](#)) and PCWG3 (bone).

If an unscheduled assessment was performed and the participant has not progressed, every attempt should be made to perform the subsequent assessments at their originally scheduled visits. This schedule is to be followed in order to minimise any unintentional bias caused by some participants being assessed at a different frequency than other participants.

All bone lesions (or sites of disease) should be identified at baseline. Their status should be followed at subsequent visits. At each visit an overall assessment of the bone lesion progression should be recorded by the investigator.

Progression on a bone scan is identified using PCWG3 as follows:

- At 8 weeks scan:  
2 or more new metastatic bone lesions are observed on the first 8-week scan compared to the baseline assessment. The confirmatory scan, performed at least 6 weeks later and preferably no later than the next scheduled visit for a bone scan (i.e., Week 16), must show 2 or more additional new metastatic bone lesions (for a total of 4 or more new metastatic bone lesions since the baseline assessment) for progression to be documented.  

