##### 4.17.2 Percentage change in tumour size (Cohort A and Cohort B)

Tumour size is the sum of the longest diameters (or short axis measurements for lymph nodes) of the target lesions. Target lesions are measurable tumour lesions. Baseline for RECIST is defined to be the last evaluable assessment prior to starting treatment. The percentage change in target lesion tumour size at each week for which data are available will be obtained for each participant taking the difference between the sum of the target lesions at each week and the sum of the target lesions at baseline divided by the sum of the target lesions at baseline multiplied by 100 (i.e., (week x - baseline)/baseline \* 100).

The absolute change and percentage change from baseline in the sum of tumour size at each assessment will be calculated. The best percentage change in tumour size from baseline will be the maximum reduction from baseline or the minimum increase from baseline in the absence of a reduction from baseline based on all post baseline assessments. The best percentage change in tumour size will include all assessments prior to the earliest of death in the absence of progression, any evidence of progression, the start of subsequent anti-cancer therapy, or the latest evaluable RECIST assessment if the participant has not died, progressed or started subsequent therapy. Change in tumour size at progression or the latest evaluable RECIST assessment (as applicable) should be included in the determination of best percentage change in tumour size.

If best percentage change cannot be calculated due to missing data (including if the participant has no TLs at baseline), a value of +20% will be imputed as best percentage change from baseline in the following situations (otherwise best percentage change will be left as missing):

- If a participant has no post-baseline assessment and has died
- If a participant has new lesions or progression of NTLs or TLs
- If a participant has withdrawn due to PD and has no evaluable TL data before or at PD

The best percentage change in TL tumour size from baseline will be summarised descriptively for molecularly eligible centrally confirmed evaluable for response set as well as evaluable for response set. The number and percentage of participants whose best percentage change data is imputed will also be presented.

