Best percentage change will be presented graphically using a waterfall plot to present each participant's best percentage change in TL tumour size as a separate bar with the bars ordered from the largest increase to the largest decrease. A reference line at the -30% change in TL tumour size level corresponds with the definition of a 'partial response' and another reference line at the +20% change in TL tumour size corresponds with the definition of 'progressive disease' will be added to the plots. All progressions will be marked with a '●' or designated with patterns or colours for ORR categories. Flagged progression on the best percentage change in TL tumour size at a particular timepoint will be based upon the NTL or new lesion progression at the same timepoint as the best percentage change. The scale in these plots will be fixed to be from -100 to 100 to avoid presenting extreme values. Values that are capped as a result of this restriction to the scale will be marked with '#'. Values are ordered in descending order with imputations due to death appearing first followed by a gap followed by all other participants. Imputed values will be clearly marked with '\*' and participants with imputation where there was a death or evidence of progression will have different shading to each other and the other participants to make it clear that these are different.

Additionally, best percentage change in tumour size will be presented graphically using waterfall plots, where best percentage change in TL tumour size as a separate bar ordered from the largest increase to the largest decrease, colour coded in respective figures by mutation categories/gene variant categories and best objective response categories marked with appropriate symbols on top of each bar.

Additional, 'spider' plots will be produced. This depicts each participant's percentage change in TL tumour size as a line over time and progression due to NTL or new lesions will be indicated (imputed data will not be included in the plots).

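### In Cohort B, participants without target lesions at baseline can enter the tumour-size summary only at +20%, and only after a bad outcome

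*SAP*

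**What the plan says.** Section 4.17.2 defines tumour size as the summed diameters of the target lesions, and percentage change as the difference from the baseline sum divided by that sum. It then gives an imputation rule: "If best percentage change cannot be calculated due to missing data (including if the participant has no TLs at baseline), a value of +20"%. Three situations trigger it:

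- "If a participant has no post-baseline assessment and has died";
- new lesions, or progression of non-target lesions (NTLs) or TLs;
- withdrawal due to progressive disease with no evaluable TL data before or at progression.

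In every other case, "otherwise best percentage change will be left as missing".

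Table 4 defines the evaluable for response set as follows: "Cohort B: All study participants with measurable disease and/or unfavourable CTC count at baseline who received at least 1 dose of study intervention". The molecularly eligible centrally confirmed version uses the same condition, and the interim analysis set is drawn from it. In Cohort A both evaluable sets require measurable disease.

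Section 4.9.1 says that the TL visit response is not applicable for a participant without measurable disease at baseline.

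On reporting, section 4.17.2 presents the number and percentage imputed and marks imputed bars on the waterfall plot. For spider plots, "imputed data will not be included in the plots".

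**The concern.** For a participant with no TLs the quantity is undefined. There is no baseline sum to divide by, and section 4.9.1 accordingly calls the TL response not applicable. Section 4.17.2 calls the same situation missing data and fills it in.

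The filling also runs in one direction. A no-TL participant enters the summary only after progression, withdrawal for progression, or death without any assessment, and always at +20%. One who stays progression-free, whose NTLs disappear, or who dies after a non-progressing assessment drops out as missing.

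Best percentage change in tumour size is a named secondary endpoint for Cohort B (section 2.1.2). At stake is whether its mean and median describe change in tumour size, or a blend of that with a progression or death indicator whose weight depends on how many participants without TLs happen to enrol.

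**Working it through.** **Can the case arise?** Yes. Table 4 admits Cohort B participants on unfavourable CTC count alone. Table 9 has rows for a TL response of NA, and Table 11 has a row for participants with neither TLs nor NTLs at baseline. Cohort A's evaluable sets exclude it.

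**What values are possible without TLs?** The three triggers give 2 x 2 x 2 = 8 yes/no combinations. Seven contain at least one trigger and give +20%; the one without any gives missing. No path gives a decrease or any other number. In the third trigger, the condition of no evaluable TL data is automatically met.

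**A contrast from the SAP's own tables.** Under Table 9, TL = NA with NTL = CR and no new lesions is an overall soft-tissue CR. That participant has no tumour-size value. A similar participant whose NTLs progress is entered at +20%.

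**Effect on the mean.** The SAP gives no figure to reproduce. Let n be the number with measured values, m their mean and k the number of no-TL participants imputed.

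- Mean after imputation = (n·m + 20k)/(n + k)
- Shift = k(20 − m)/(n + k)

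The planned Cohort B size is 27 (section 3.1.1). The split by TL status, m and k are assumptions.

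| n with TLs (of 27) | k | Shift, m = −5% | Shift, m = −15% |
|---|---|---|---|
| 24 | 1 to 3 | +1.0 to +2.8 | +1.4 to +3.9 |
| 20 | 2 to 6 | +2.3 to +5.8 | +3.2 to +8.1 |
| 14 | 3 to 9 | +4.4 to +9.8 | +6.2 to +13.7 |

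For example, n = 14, k = 9, m = −15 gives 9 x 35/23 = 13.7, so −15% becomes −1.3%. With n = 24, k = 1, m = −5, the shift is 1 x 25/25 = 1.0.

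**Effect on the median.** By simulation (normal values, assumed SD of 25 points, 100,000 runs), the median shift is +1.3 to +3.9 for n = 24, k = 1 to 3. For n = 14, k = 3 to 9, it is +6.7 to +19.8 at m = −5% and +6.7 to +22.0 at m = −15%.

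**Which outputs are affected?** Mainly the molecularly eligible centrally confirmed evaluable for response set and the interim analysis set. For the wider evaluable for response set, Table 6 says "Only spider plot will be provided for this analysis set", and spider plots omit imputed values. Section 4.17.2 nevertheless promises a descriptive summary for that set too, a separate inconsistency.

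**Bone progression.** Section 4.9.4 states: "Bone lesions will be assessed by bone scan and will not be part of the RECIST v1.1 malignant soft tissue assessment". The same section uses the term new lesions for bone hot-spots. The SAP does not say whether bone-only progression meets the new-lesion trigger.

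**The case against.** The rule is explicit: the no-TL case is named and the value, triggers and default are fixed in advance. It is conservative, since it makes the drug look worse and cannot create a false efficacy signal in a study without formal hypothesis tests. It is largely disclosed: the imputed count is reported, imputed bars carry a mark with different shading for death and progression, and no measured bar changes. Section 4.17.4 first uses the full evaluable sets for radiological response and adds a measurable-disease subset, so it is not a clean precedent for restriction. Dependence on outcome also remains for participants who have TLs but no follow-up, whom the fix leaves under the +20% rule. The magnitudes rest on assumptions.

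Much of this is fair, and it limits the severity. It does not remove the point. A conservative value suits a quantity that exists but was not observed, not one that is undefined. Disclosure lets a reader separate bars on the waterfall plot, but no mean or median without the imputed values is specified, and the imputed count is not split between no TLs at baseline and TLs with missing follow-up. Section 4.17.4 is mixed, but its closing paragraph does use a measurable-disease denominator, so the subset is already needed. The bone ambiguity is minor: for a no-TL participant it changes the value only if there is no withdrawal for progression and no other trigger.

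**Conclusion.** The concern holds, for Cohort B only. A participant without baseline TLs can contribute +20% or nothing to an endpoint that is undefined for them, and contributes only after a bad outcome. The direction is certain for the mean: upwards whenever the measured mean is below +20%. The size is not known, because the SAP gives neither the number without TLs nor the distribution of change. Over the assumed scenarios the mean shifts by 1.0 to 13.7 points, and the effect is small if few lack TLs. The endpoint is secondary and descriptive, and the Cohort B futility guidance rests on composite response (section 4.14). The text should be corrected, but no trial decision rule in the SAP depends on it.

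**What to change.** In section 4.17.2:

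- Restrict the Cohort B tumour-size summary and waterfall plots to participants with at least one TL at baseline.
- Delete the parenthesis that extends the imputation to participants with no TLs, and report their number separately.
- Keep the +20% rule only for participants with baseline TLs but no evaluable post-baseline TL data.
- State whether PCWG3 bone progression counts as a new lesion under that rule.
- Reconcile the Table 6 spider-plot footnote with the descriptive summary promised for the evaluable for response set.

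The cost is a wording change and a subset flag that section 4.17.4 already needs. The Cohort B waterfall plot may have fewer bars, but radiological progression in those participants remains captured in rPFS and best overall radiological response.

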#### 4.17.3 Progression free Survival (Cohort A)

PFS is defined as the time from first dose until the date of objective disease progression or death (by any cause in the absence of progression) regardless of whether the participant withdraws from study therapy or receives another anti-cancer therapy prior to progression (i.e. date of PFS event or censoring – date of first dose + 1). Participants who have not progressed or died at the time of analysis will be censored at the time of the latest date of assessment from their latest evaluable RECIST

assessment. However, if the participant progresses or dies after two or more missed visits, the participant will be censored at the time of the latest evaluable RECIST 1.1 assessment prior to the two missed visits. NE is not considered a missed visit.

Given the schedule of RECIST assessments (i.e., every 8 weeks for the first year and every 12 weeks there after until a confirmed progression) two missing visits will equate to 18 weeks in the first year (i.e.,  $2 \times 8 = 16$  weeks + 1 week for early assessment + 1 week for a late assessment = 18 weeks), 26 weeks in the subsequent years (i.e.,  $2 \times 12 = 24$  weeks + 1 week for early assessment + 1 week for a late assessment = 26 weeks) after the first treatment allowing for early and late visits.

If the participant has no evaluable visits or does not have baseline data, they will be censored at Day 1 unless they die within 17 weeks (16 weeks plus 1 week allowing for a late assessment within the visit window).

The PFS time will always be derived based on scan/assessment dates and not visit dates.

RECIST assessments/scans contributing towards a particular visit may be performed on different dates. The following rules will be applied:

- For investigational assessments, the date of progression will be determined based on the **earliest** of the dates of the component that triggered the progression
- When censoring a participant for PFS the participant will be censored at the **latest** of the dates contributing to a particular overall visit assessment

Note: for TLs only the latest scan date is recorded out of all scans performed at that assessment for the TLs and similarly for NTLs only the latest scan date is recorded out of all scans performed at that assessment for the NTLs.

Analyses of PFS will be based upon the molecularly eligible centrally confirmed set and safety analysis set.

A time to progression swimmer plot and a Kaplan-Meier plot of PFS will be presented. Median PFS with respective 80% CIs will be estimated using the Kaplan-Meier technique. Summaries of the number and percentage of participants experiencing a PFS event, and the type of event (progression or death) will be provided along with the proportion of participants alive and progression free at three months, six months, nine months and twelve months calculated using the Kaplan-Meier (KM) technique. Median and range of follow up duration for censored participants will be provided as well.

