# Parexel International

AstraZeneca

D5339C00001

Statistical Analysis Plan

C1D8	Day 8	C1D1+7 ( $\pm 1$ ) days	C1D1+7 (-3/+2) days OR C1D5 to C1D10
C1D14	Day 14	C1D1+13 ( $\pm 2$ ) days	(C1D1+13) - 3 days to C2D1 - 2 days OR C1D11 to C2D1 - 2 days
C2D1 [b]	Day 29	C2D1 - 1 day to C2D1	C2D1 - 1 day to C2D1 + 3 days (C2D4)
C2D8	Day 36	C2D1+7 ( $\pm 1$ ) days	C2D1+7 (-3/+2) days OR C2D5 to C2D10
C2D14	Day 42	C2D1+13 ( $\pm 2$ ) days	(C2D1+13) - 3 days to (C3D1 -2) days OR C2D11 to C3D1 - 2 days
CxD1 [b],[c]	Day 1 + (x-1)*28 days	CxD1 - 1 day to CxD1	CxD1 - 1 day to CxD1 + 3 days (CxD4)
IP DISC	-	IP Disc date +14 days	IP Disc date + 14 days
Safety follow-up	IP DISC + 30 ( $\pm 7$ ) days	IP Disc date + 14 days to IP Disc date + 37 days	IP Disc date + 14 days to IP Disc date + 37 days

[a] Any value up to Day 1 including pre-treatment time will be considered as baseline. The handling of duplicate baseline value will be explained in Section 4.2.

[b] The start date of dosing of each cycle (CxD1) should be taken from the exposure data.

[c]  $X \geq 3$ .

eCRF - electronic Case Report Form. IP DISC - Investigational Product discontinuation.

For summaries showing the maximum or minimum values, the maximum/minimum value recorded on treatment will be used (regardless of where it falls in an interval and if it was collected at a scheduled or unscheduled visit).

Listings will display all values contributing to a time point for a participant; they will also highlight the value for the participants that will be used in the summary table, wherever possible.

RECIST and bone lesion (for cohort B only) assessments for all participants will be assessed every 8 weeks ( $\pm 7$  days) after Cycle 1 day 1 for the first year and every 12 weeks ( $\pm 7$  days) thereafter until objective disease progression by RECIST 1.1 (for cohort A) or radiological progression (for cohort B). Analysis visit windows will be assigned to the RECIST (cohort A) / radiological (cohort B) overall visit response assessments so that all assessments are allocated to the nearest scheduled time point. If more than one assessment falls in a given visit window, then the value closest to the protocol scheduled time point will be used. In the event of an equidistant time point, the earlier time point will be used.

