### Table 3: RECIST/bone lesion Assessments Visit Windows

(W: Week)

Week Number	Days after first dose of the treatment (Cycle 1 Day 1)	Visit Label	Window	Visit Window
8	57	W8		[Day 50; Day 84]
16	113	W16		[Day 85; Day 140]
24	169	W24		[Day 141; Day 196]
32	225	W32		[Day 197; Day 252]
40	281	W40		[Day 253; Day 308]
48	337	W48		[Day 309; Day 364]
56	393	W56		[Day 365; Day 434]
68	477	W68		[Day 435; Day 518]
80	561	W80		[Day 519; Day 602]
92	645	W92		[Day 603; Day 686]
104	729	W104		[Day 687; Day 770]
....	....	....		.....
Until RECIST 1.1 progression				

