#### 4.17 Secondary Efficacy Variables

##### 4.17.1 Duration of Response (Cohort A)

Duration of response will be defined as the time from the date of first documented response (which is subsequently confirmed) until date of documented progression or death in the absence of disease progression (i.e., date of PFS event or censoring – date of first response + 1). The end of response should coincide with the date of progression or death from any cause used for the PFS endpoint. The time of the initial response will be defined as the latest of the dates contributing towards the first visit that was PR or CR that was subsequently confirmed.

If a participant does not progress following a response, then their duration of response will use the PFS censoring time (see [Section 4.17.3](#)).

Descriptive data will be provided for the duration of response in responding participants, including the associated Kaplan-Meier estimate of median duration of response, where there are sufficient number of responders based on molecularly eligible centrally confirmed evaluable for response set as well as evaluable for response set. A Kaplan-Meier plot and a swimmer plot will also be provided.

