**4.17.8 rPFS (Cohort B)**

Radiological PFS is defined as the time from the start of treatment until the date of objective radiographic disease progression or death. Participants who have not progressed (i.e., who have a CR, PR or SD by RECIST 1.1, and nonprogressive disease by PCWG-3) at the time of analysis will be censored, the latest date of their last evaluable RECIST 1.1 assessment or bone scan assessment that showed fewer than 2 new lesions. However, if the 2 or more consecutive scheduled radiographic assessments immediately prior to progression or death were missing, the participant will be censored at the time of the latest evaluable RECIST 1.1 and bone scan assessment prior to the 2 or more missed assessments. If the participant has no evaluable visits or does not have baseline data, they will be censored at Day 1 unless they die within 2 visits of baseline (in which case the participant’s date of death will be used). The rPFS time will always be derived based on scan/assessment dates, not visit dates. When the investigator is in doubt as to whether progressive disease has occurred and therefore reassesses the participant at a later date, the date of the initial scan should be declared as the date of progression if the repeat scans confirm progression. Analyses of rPFS will be based upon the molecularly eligible and centrally confirmed set and safety analysis set. KM plots of rPFS will be presented. Summaries will include the median rPFS with respective 80% CIs calculated using the Kaplan-Meier technique. Summaries will also provide the number and percentage of participants experiencing a rPFS event, and the type of event (radiological progression or death), along with the proportion of the participants alive and progression free at three months, six months, nine months and twelve months using KM technique. A 80% confidence interval for the survival estimates will be provided.

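### Does the two-missed-visit censoring rule for PFS fail when scans change from 8-weekly to 12-weekly?

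*SAP*

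**What the plan says.** Section 4.17.3 of the SAP moves the PFS date back to the last evaluable assessment "if the participant progresses or dies after two or more missed visits". It then translates two missed visits into weeks, using the scan interval plus one week for an early and one week for a late assessment: "two missing visits will equate to 18 weeks in the first year" (2 × 8 + 1 + 1) and "26 weeks in the subsequent years" (2 × 12 + 1 + 1), with the years counted from first treatment.

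The schedule is in section 4.3.2: every 8 weeks "for the first year and every 12 weeks" after that. Table 3 lists the visits. W48 is Day 337 with window "Day 309; Day 364", W56 is Day 393, and W68 is Day 477 with window "Day 435; Day 518". The last 8-week step (W48 to W56) therefore ends after Day 365, and the first 12-week step is W56 to W68.

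The Cohort B rule in section 4.17.8 uses no week figures. It applies "if the 2 or more consecutive scheduled radiographic assessments immediately prior to progression or death were missing". Duration of response in Cohort A (section 4.17.1) inherits the PFS date: "The end of response should coincide with the date of progression or death from any cause used for the PFS endpoint".

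**The concern.** Two limits are given for a schedule that has three kinds of consecutive interval pairs: 8 + 8, 8 + 12 and 12 + 12 weeks. The mixed pair, which arises after a last scan at W48, has no figure. The text also does not spell out which date must fall in the first year: the last scan, the missed visits or the event.

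A programmer who works from the week figures alone could go wrong in either direction. With 18 weeks after W48, progression at W68 would be censored although only W56 was missed. With 26 weeks, a death some time after W68 was also missed would be kept as an event, although the rule would censor it. Two programmers might then classify the same participant differently. The outputs exposed are the PFS event count, the late part of the Kaplan-Meier curve and duration of response.

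**Working it through.** **Inputs.** Table 3 target days: W32 = 225, W40 = 281, W48 = 337, W56 = 393, W68 = 477, W80 = 561. Scan tolerance is ±7 days (section 4.3.2). The limits are 18 weeks (126 days) and 26 weeks (182 days).

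**The plan's own figures.** Limit = (second missed visit + 7 days) − (last scan − 7 days).
- Last scan W8 (Day 57), W16 and W24 missed: (169 + 7) − (57 − 7) = 126 days = 18 weeks. The same holds through W40.
- Last scan W56, W68 and W80 missed: (561 + 7) − (393 − 7) = 182 days = 26 weeks. The same holds for later scans.
- Last scan W48, W56 and W68 missed: (477 + 7) − (337 − 7) = 154 days = 22 weeks. Neither stated figure equals this.

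**Scheduled scans, with the missed visits setting the year.**
- W48 to W68, one scan missed: W56 is after Day 365, so 26 weeks applies. The gap is 140 days (20 weeks), at most 484 − 330 = 154 days (22 weeks). The event is kept, correctly.
- W48 to W80, W56 and W68 missed: the gap is at least 554 − 344 = 210 days (30 weeks). It is censored, correctly.
- W32 to W56, W40 and W48 missed: both are in year one, so 18 weeks applies. The gap is at least 386 − 232 = 154 days (22 weeks). It is censored, correctly.
- W40 to W68, W48 and W56 missed: the pair straddles the year. The shortest gap is 470 − 288 = 182 days. At 18 weeks every case is censored, correctly. At 26 weeks, only the single combination at exactly 182 days escapes.

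All Table 3 pairs from W8 to W104 were enumerated with up to three missed scans and 15 × 15 = 225 date combinations per pair, censoring when the gap exceeds the limit:

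| What sets the limit | Misclassified |
|---|---|
| Missed visits, W48/W56 at 18 weeks | none |
| Missed visits, W48/W56 at 26 weeks | W40 to W68: 1 of 225 |
| Date of last scan | W48 to W68: 224 of 225 |
| Date of event | W32 to W56: 225 of 225; W40 to W68: 1 of 225 |

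**Deaths, which follow no schedule.**
- After W48, the 26-week limit ends on Day 337 + 182 = 519, while W68 ± 7 days closes on Day 484. The limit overruns by 35 days. The usual overrun is 7 days (W8: 57 + 126 = 183 against 169 + 7 = 176), so the excess is 28 days.
- After W40, 18 weeks ends on Day 407 against W56 closing on Day 400, the usual 7 days. At 26 weeks it ends on Day 463, an overrun of 63 days. Both intervals are 8 weeks here, so the plan's formula gives 2 × 8 + 2 = 18.

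**Unscheduled progression after W48.** Section 4.3.2 allocates each assessment to the nearest scheduled visit, and Table 3 runs W68 to Day 518. A progression scan on Days 485 to 518 is therefore a W68 assessment with only W56 missed, and keeping it is right.

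**Participants affected.** The SAP gives no rates. Assumed here: PFS at 48 weeks 5–20%, PFS at 32 weeks 10–35%, two consecutive scans missed 1–3%, n = 25.
- W48, then two missed: 25 × 0.05 × 0.01 = 0.01 to 25 × 0.20 × 0.03 = 0.15.
- W40, then two missed: no more participants can be progression-free at week 40 than at week 32, so at most 25 × 0.35 × 0.03 = 0.26.

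The upper figures sum to 0.41. Both overstate the effect, because the death must also fall in the affected interval. In addition, the cut-off is about 6 months after the 25th participant (section 3.2, Table 1), so later enrolees will not reach Day 393.

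**The case for a change.** The best argument for a change is that the SAP states the week figures as equivalents of two missed visits, so a programmer may fairly use them. If the limit is chosen by the date of the last scan or of the event, a whole scan pattern is misclassified (224 or 225 of 225 combinations). The team is unblinded, and with few participants at risk late, one reclassification would show in the curve. A 22-week limit for W48 costs one sentence and restores the usual 7-day overrun.

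Part of this stands. The 22-week figure is absent, and W48/W56 is not assigned. The large error counts do not carry over, because they need a selector that the text does not use. The sentence attaches the year to the missing visits, counted from first treatment.

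A related objection is that a visit can be called missed at +7 days (Day 484 for W68) or at the end of its Table 3 window (Day 518). That is true, but it is not specific to the schedule change. After W8 the 18-week limit ends on Day 183, while the W24 window runs to Day 196.

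**Conclusion.** No change is needed. This is a missing detail in a conversion that only illustrates the rule. The rule counts missed visits, Table 3 lists the visits, and an analyst who counts them gets the right classification without the week figures. One who uses the week figures as the sentence reads goes wrong for scheduled scans in at most 1 of 225 date combinations of a single pattern.

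The residue is deaths on about Days 485 to 519 after a W48 scan with W56 and W68 both missed, plus the straddling W48/W56 pair, which the plan's own formula settles at 18 weeks. Together they involve fewer than one participant. That size rests on the assumed progression-free and missed-scan rates, but the upper values used still total only 0.41 of 25.

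The three- and six-month PFS proportions cannot move. The W48 case cannot move the nine-month proportion either, because it changes nothing before about Day 337. The late curve, the twelve-month proportion and an occasional duration of response could shift slightly. PFS is a secondary endpoint, and section 4.10 plans no formal hypothesis test, so no conclusion depends on it.
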